PFS6	Progression-free Survival at 6 months
PFS12	Progression-free Survival at 12 months
PIAI	Prognostic Index for AITL
PIT	Prognostic Index for Peripheral T-cell lymphoma

PK	Pharmacokinetics
PR	Partial Remission
PS	Performance Status
RBC	Red Blood Cell
R/R	Relapsed/Refractory
SAE(s)	Serious Adverse Event(s)
SD	Stable Disease
SOC	System Organ Class
SPD	Sum of the Product of the Diameters
StD	Standard Deviation
TTP	Time to Tumor Progression
ULN	Upper Limit of Normal
v	Version
WBC	White Blood Cells
WHO	World Health Organization
wk	Week

1 STUDY RATIONALE

Angioimmunoblastic T-cell lymphoma (AITL) is the second most common form of peripheral T-cell lymphoma (PTCL), accounting for approximately 20% of PTCLs and 2% of non-Hodgkin lymphomas (NHL). In the United States, the incidence is approximately 0.05 cases per 100,000 person years. The disease is more common in Europe (29% of PTCL cases) than in the United States or Asia.

The clinical course of AITL varies, with occasional spontaneous remissions. Nevertheless, the prognosis of the disease is dismal, with median survival < 3 years, and with 20–30% of long-term survivors. Different clinical risk factors as well as biological parameters have been described as prognostic factors. In a retrospective study of 157 cases of AITL, a multivariate analysis showed the following covariates as adversely associated with prognosis: male gender, anemia and the presence of mediastinal lymphadenopathy.

Other systems such as the International Prognostic Index (IPI) or the prognostic index for peripheral T-cell lymphoma (PIT) were of limited value in this disease. Recently, a risk model for AITL (prognostic index for AITL, PIAI) was designed based on the following adverse covariates: age > 60 years, performance status \geq 2, extranodal sites > 1, B-symptoms, and platelet count < 150,000/mL. The simplified PIAI had a low-risk group (zero to one factors) with a 5-year survival of 44%, and a high-risk group (two to five factors) with a 5-year survival of 24%.

In phase I studies conducted with plitidepsin, the schedule consisting of 1-hour i.v. infusion given weekly on D1, 8 and 15 q4wk was found to be the most convenient for patients with NHL. An exploratory phase II clinical trial (APL-B-013-02) was conducted to evaluate the efficacy, tolerability and pharmacokinetics of this weekly plitidepsin schedule at a starting dose of 3.2 mg/m² in patients with relapsed/refractory (R/R) aggressive NHL. This phase II trial included two cohorts: patients with non-cutaneous PTCL and patients with other aggressive lymphomas. No remissions were found in the cohort of 33 patients with other aggressive lymphomas. However, interesting antitumor activity was observed in 29 evaluable patients from the non-cutaneous PTCL cohort: ORR was 20.7% (95% CI, 8.0–39.7%) and SD rate was 20.7%.

Several studies have shown that plitidepsin induces apoptosis in a cell type- and dose-dependent manner, and these effects are related to the induction of early oxidative stress, the activation of Rac1 GTPase and the inhibition of protein phosphatases, which in conjunction cause the sustained activation of JNK and p38 MAPK. The final consequence is the triggering of the mitochondrial apoptotic pathway with caspase 9 and caspase 3 activation. Additional effects may be mediated by indirect effects on the cell microenvironment, mainly mediated by antiangiogenic properties and indirect effects on monocyte-derived cells, including follicular dendritic cells.

2 STUDY DESIGN

Prospective, multicenter, phase II clinical trial.

The aim of this clinical trial is to determine the efficacy of plitidepsin in patients with relapsed/refractory AITL. A total of 60 patients will receive plitidepsin. The primary endpoint will be the ORR according to the Lugano classification response criteria per independent central review.

An Independent Review Committee (IRC) consisting of medical specialists (radiologists and hematologists) who are directly involved in the care of patients with AITL but do not take part in this trial as investigators or sub-investigators, will review all efficacy data and will assign the date of objective response or progression/censoring according to their independent evaluation.

Two futility analyses of the primary endpoint (ORR according to Lugano classification response criteria and per IRC) are planned around six months after approximately 25% and 50% of eligible patients (i.e., 15 and 30 patients respectively with AITL confirmed by central pathological review) have been treated. Two or less responders out of 15 patients or seven or less responders out of 30 patients, according to boundaries and sample size assumptions, will mean that the alternative hypothesis could be rejected, and thus recruitment might be stopped at the time of the first or second futility analysis, respectively. Otherwise, accrual will continue to a total of 60 patients with AITL confirmed by central pathological review. This decision will be taken at the time by an Independent Data Monitoring Committee (IDMC). The IDMC, which will include specialists in PTCL supported by a medical statistician, will review data provided by the Investigators, the IRC efficacy assessments and safety information and will advise whether the study should continue. Recruitment can continue during the review period.

If there are 19 or more responders over the total of 60 patients, the efficacy of plitidepsin will be considered as clinically relevant in AITL patients.

Operational details for the IRC and IDMC will be detailed in the corresponding charters.

3 OBJECTIVES AND ENDPOINTS

3.1 Primary objective

- To evaluate the efficacy of plitidepsin on the basis of overall response rate (ORR) in patients with relapsing/refractory angioimmunoblastic T-cell lymphoma (AITL).

3.2 Secondary objectives

- To evaluate other efficacy endpoints (time-to-event parameters: duration of response [DoR], progression-free survival [PFS], PFS at 6/12 months [PFS6/PFS12], inpatient PFS/TTP, overall survival [OS] and OS at 6/12 months [OS6/OS12]).
- To evaluate the safety profile of plitidepsin in this patient population.
- To characterize the pharmacokinetics (PK) of plitidepsin.
- To identify biomarkers that may be predictive of plitidepsin activity.

3.3 Endpoints

Primary endpoint:

- Overall response rate (ORR), defined as the percentage of patients with remission, either complete (CR) or partial remission (PR), according to the Lugano classification response criteria per independent central review. An external IRC will assign the objective response and a progression or censoring date for each patient.

Secondary endpoints:

- ORR per investigator.
- CR rate, defined as the percentage of patients with complete remission according to the Lugano classification response criteria per independent central review and investigator assessment.
- Duration of response (DoR), defined as the time from the date when the remission criteria (PR or CR, whichever is first achieved) are fulfilled to the first date when PD, recurrence or death (due to any cause) is documented. Response will be assessed according to the Lugano classification response criteria per independent central review and investigator assessment.
- Progression-free survival (PFS), defined as the time from the date of first drug administration to the date of PD, death (of any cause), or last tumor evaluation; both independent central review and investigator assessment will be used for the determination of PFS.

- Progression-free survival at 6/12 months (PFS6/PFS12), defined as the Kaplan-Meier estimate of the percentage of patients who are progression-free at six/twelve months after first drug administration; both independent central review and investigator assessment will be used for the determination of PFS.
- Inpatient PFS/TTP, defined as the ratio of PFS achieved with the experimental treatment *versus* the prior last TTP in the R/R setting.
- Overall survival (OS), defined as the time from the date of first dose to the date of death (of any cause) or last patient contact.
- Overall survival at 6/12 months (OS6/OS12), defined as the Kaplan-Meier estimate of the percentage of patients who are live at six/twelve months after first drug administration.
- Treatment safety [AEs, serious adverse events (SAEs) and laboratory abnormalities] graded according to the NCI-CTCAE, v. 4. Dose reductions, skipped doses or dose delays required due to treatment-related AEs, and reasons for treatment discontinuations will be analyzed.
- Pharmacokinetics (PK), samples for PK analysis will be obtained during Cycle 1 exclusively.
- Exploratory biomarker analysis, correlation of efficacy with molecular markers (targets/pathways) related to the mechanism of action of plitidepsin or to the disease.

4 PATIENTS EVALUABILITY CRITERIA

The study population will include patients who have relapsed or refractory AITL confirmed by local pathological assessment. To be included in this study, the patients must meet all inclusion criteria and no exclusion criteria.

4.1 Analysis sets definitions

“All Included Patients” analysis set is defined as all patients who are included in the study (excluding patients who signed informed consent but are classified as screening failures), independent of whether they received the study drug.

“All Treated Patients” analysis set is defined as all included patients who receive at least part of one dose or infusion of plitidepsin.

“Per Protocol Patients” analysis set is defined as all eligible and treated patients with AITL diagnosis confirmed after central pathological review.

“All Evaluable Patients” analysis set is define as all eligible patients with AITL diagnosis confirmed after central pathological review who receive at least two plitidepsin cycles in which at least two complete infusions have been administered and had at least one disease assessment as well as in patients who discontinue treatment without Cycle 3 tumor assessment after at least two plitidepsin infusions due to disease progression (PD) (or death due to PD) or toxicity (or death due to toxicity), defined as “early PD” and “treatment failures” respectively.

“All Responder Patients” analysis set is defined as all patients with CR or PR as overall best response.

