## **5.3 ADDITION OF PATIENTS**

All eligible and treated patients with AITL diagnosis confirmed after central pathological review will be included in the main efficacy analyses (primary and secondary endpoints).

If a patient is treated but AITL diagnosis is not finally confirmed after central pathological review of the biopsy (even if inclusion was approved on the basis of the local histopathological report) then an additional patient will be included. Specifically, cases with features of follicular-PTCL and PTCL-NOS with TFH phenotype or with features of progression/transformation from AITL to Diffuse Large B-cell Lymphoma need to be excluded from the main efficacy analysis so additions are permitted in the event such patients are included before (or in spite of) central pathological exclusion. All patients without central confirmation will be excluded from the main efficacy analyses but included in safety analyses and, as supportive analyses, efficacy assessments will be done including all treated patients.

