## **8. STUDY EVALUATIONS**

### **8.1 EFFICACY**

The aim of this clinical trial is to determine the antitumor activity of plitidepsin in patients with AITL. The primary endpoint will be the ORR according to the Lugano classification response criteria per independent central review (see Section [3.1](#) and [Appendix 2](#) for more details). Secondary endpoints of efficacy include ORR per investigator assessment (IA), CR, DoR, PFS, PFS6/12, OS and OS6/12 (see Section [3.2](#) for more details).

All eligible and treated patients with AITL diagnosis confirmed after central pathological review will be included in the main efficacy analyses (primary and secondary endpoints). If a patient is treated but AITL diagnosis is not finally confirmed after central pathological review of the biopsy (even if inclusion was approved on the basis of the local histopathological report) then an additional patient will be included. Specifically, cases with features of follicular-PTCL and PTCL-NOS with TFH phenotype or with features of progression/transformation from AITL to Diffuse Large B-cell Lymphoma need to be excluded from the main efficacy analysis so additions are permitted in the event such patients are included before (or in spite of) central pathological exclusion.

Supportive efficacy analyses will be assessed in all treated patients and in all evaluable patients—defined as eligible patients who receive at least two plitidepsin cycles in which at least two complete infusions have been administered and had at least one disease assessment—as well as in patients who discontinue treatment without Cycle 3 tumor assessment after at least two plitidepsin infusions due to disease progression (PD) (or death due to PD) or toxicity (or death due to toxicity) defined as “early PD” and “treatment failures” respectively.

Patients without confirmation of AITL by central pathological review be excluded from the main efficacy analyses but, as supportive analyses, efficacy assessment will be done including all treated patients.

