4.2 Efficacy populations

The “All Included Patients” analysis set will be used to show demographic and other baseline characteristics.

The “Per Protocol Patients” analysis set will be used for the primary endpoint analysis of ORR by IRC and for the secondary analyses of ORR by investigator assessment, CR rate and PFS analyses, as well as for OS analyses.

The “All Evaluable Patients” and “All Treated Patients” analysis sets will be used for the secondary endpoint analyses of ORR by IRC, ORR by investigator assessment, CR rate and PFS analyses, as well as for OS analyses.

The “All Responder Patients” dataset will be used for the duration of response (DoR) calculation.

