6.2.2 Secondary analyses

Time to event endpoints will be used in an exploratory way.

Binomial estimates with exact 95% CIs will be calculated for the analysis of **complete remission rate** in the "Per Protocol Patients", "All Evaluable Patients" and "All Treated Patients" analysis sets by independent review and investigator assessment.

Duration of response will be analyzed according to the Kaplan-Meier method in "All Responder Patients" analysis set by independent review and investigator assessment.

Time to response is defined as the time, in months, from the date of first drug administration to the first documentation of response method in "All Responder Patients" analysis set by independent review and investigator assessment.

PFS analysis will be performed in "Per Protocol Patients", "All Evaluable Patients" and "All Treated Patients" analysis sets according to the Kaplan-Meier method by independent review and investigator assessment. The concordance between the IRC and investigator evaluation of response and PFS will be shown using counts and percentages.

OS analysis will be performed in “Per Protocol Patients”, “All Evaluable Patients” and “All Treated Patients” analysis sets according to the Kaplan-Meier.

Univariate evaluation of the influence of different prognostic factors on the main efficacy endpoints will be performed. If appropriate, univariate analyses will include prognostic factors/covariates widely reported and recognized by hematologist such as: sex, age at diagnosis, baseline ECOG, Body Surface Area, Ann arbor, extranodal disease, bone marrow involvement, B symptoms, baseline LDH xULN, bulky lesion, IPI, PIT, PIAI, Relapse or refractory, number of prior lines of treatment, previous SCT or time from last PD before inclusion. Further covariates could be included upon hematologist criteria.

Cox proportional hazard models for PFS and OS, and logistic regression models for ORR will include the prognostic factors specified for the univariate analysis. More relevant and explanatory covariates from the univariate analysis will be included in the multivariate analyses (p-value < 0.10). Prognostic factors with more than 10% missing values will be excluded in the multivariate analyses.

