Table 11.3.2.11 ORR – Concordance between Independent Review assessment and Investigator assessment (“Per Protocol Patients” population)

Response by IRC	Response by Investigator assessment				
	CR	PR	SD	PD	NE
CR					
PR					
SD					
PD					
NE					

Table 11.3.2.12 CR rate estimates by the Lugano classification response criteria (Independent Review assessment and “Per Protocol Patients” population)

	Proportion	Lower 95% limit	Upper 95% limit
CR rate	X.X	X.X	X.X

Binomial exact estimator and 95% confidence interval

Table 11.3.2.13 CR rate estimates by the Lugano classification response criteria (Independent Review assessment and “All Evaluable Patients” population)

	Proportion	Lower 95% limit	Upper 95% limit
CR rate	X.X	X.X	X.X

Binomial exact estimator and 95% confidence interval

Table 11.3.2.14 CR rate estimates by the Lugano classification response criteria (Independent Review and “All Treated Patients” population)

	Proportion	Lower 95% limit	Upper 95% limit
CR rate	X.X	X.X	X.X

Binomial exact estimator and 95% confidence interval

Table 11.3.2.15 CR rate estimates by the Lugano classification response criteria (Investigator assessment and “Per Protocol Patients” population)

	Proportion	Lower 95% limit	Upper 95% limit
CR rate	X.X	X.X	X.X

Binomial exact estimator and 95% confidence interval

Table 11.3.2.16 CR rate estimates by the Lugano classification response criteria (Investigator assessment and “All Evaluable Patients” population)

	Proportion	Lower 95% limit	Upper 95% limit
CR rate	X.X	X.X	X.X

Binomial exact estimator and 95% confidence interval

Table 11.3.2.17 CR rate estimates by the Lugano classification response criteria (Investigator assessment and “All Treated Patients” population)

	Proportion	Lower 95% limit	Upper 95% limit
CR rate	X.X	X.X	X.X

Binomial exact estimator and 95% confidence interval

Table 11.3.2.18 Duration of response (Independent Review assessment and “All Responder Patients” population)

N	X
Events	X
Censored	X
Median DoR	X.X

Kaplan-Meier plot will be also shown (Figure 11.3.2.18)

Table 11.3.2.19 Duration of response (Investigator assessment and “All Responder Patients” population)

N	X
Events	X
Censored	X
Median DoR	X.X

Kaplan-Meier plot will be also shown (Figure 11.3.2.19)

Table 11.3.2.20 Time to response (Independent Review assessment and “All Responder Patients” population)

N	X
Median	X
Minimum	X
Maximum	X.X

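### Duration of response is planned only in all responders, with no central AITL confirmation required, although the protocol restricts the main secondary-endpoint analyses to confirmed patients

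*SAP*

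**What the plan says.** SAP 4.1 makes central confirmation of AITL a condition of two sets, Per Protocol and All Evaluable. The All Responder Patients set has no such condition: it "analysis set is defined as all patients with CR or PR as overall best response". SAP 4.2 assigns ORR, CR rate, PFS and OS to Per Protocol, with All Evaluable and All Treated as further sets. DoR is treated differently: the All Responder Patients "dataset will be used for the duration of response (DoR) calculation".

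SAP 6.1.2 repeats this assignment. SAP 6.2.2 does too ("Duration of response will be analyzed according to the Kaplan-Meier method in" the All Responder Patients set) and uses the same set for time to response. The only table shells are 11.3.2.18 to 11.3.2.21, beginning with "Table 11.3.2.18 Duration of response (Independent Review assessment and" the All Responder population. SAP 6.2.2 also states: "Time to event endpoints will be used in an exploratory way".

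Protocol 5.3 says that eligible, treated patients "with AITL diagnosis confirmed after central pathological review will be included in the main efficacy analyses (primary and secondary endpoints"). It adds: "All patients without central confirmation will be excluded from the main efficacy analyses but included in safety analyses". Protocol 8.1 repeats the rule for patients lacking confirmation and allows a wider analysis only in a secondary role: "as supportive analyses, efficacy assessment will be done including all treated patients". Protocol 3.2 and 8.1 both list DoR as a secondary endpoint.

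**The concern.** In a single-arm trial, DoR is read next to ORR: how many responded, and for how long. Here the two would rest on different patients. The DoR set under independent review contains every responder counted in the primary ORR plus any responder whose diagnosis was not centrally confirmed, so its N can exceed the ORR numerator.

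The added patients are a mixed group. Some may have another lymphoma, which is why the protocol excludes them. Others may have AITL but no evaluable specimen, which Protocol 5.2.2 does not count as a deviation. The plan expects such patients: inclusion rests on central review of the local report, unconfirmed patients are replaced (Protocol 5.3), and SAP Listing 10.2.7 is set up to list them.

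PFS and OS are just as exploratory as DoR, and both still have Per Protocol tables. The gap is specific to the analyses of responders.

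**Working it through.** The documents give no DoR figure for this trial, so the check is a comparison of the texts followed by an estimate of scale.

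**Texts side by side**

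| Analysis | Centrally confirmed set planned? | Other sets |
|---|---|---|
| ORR, CR rate, PFS, OS | Yes (Per Protocol) | All Evaluable, All Treated |
| DoR | No | All Responder only |
| Time to response | No | All Responder only |

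The protocol requires confirmed patients for the main analysis of every secondary endpoint. DoR is listed there, so its row conflicts with the protocol. Time to response is introduced in SAP 6.2.2 and is not a protocol endpoint; for it the point is consistency with the other SAP efficacy analyses.

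The responder definition also omits eligibility, which Per Protocol requires, and does not say whose best response counts. The table titles do separate independent review from investigator assessment.

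**The plan's nearest figure.** For 19/60 = 31.7%, the exact 95% interval is 20.26% to 44.96%, matching the stated 20.3%-45.0% (SAP 5). It is computed in confirmed patients and does not depend on the responder set.

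**How many extra responders**

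Inputs:
- 60 confirmed patients (SAP 5).
- Confirmed responders: 19 (the success threshold) to 24 (40% of 60, the alternative).
- Share not confirmed, u: assumed 10-30%. Protocol section 3 cites about 30% discordance between referring and final pathology. That is probably an upper bound here, because local reports are centrally reviewed before inclusion.
- Response rate in unconfirmed patients, r: 15%, from the earlier trial in Protocol Table 1. PTCL responders 6/29 minus AITL responders 3/9 leaves 3/20.

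Formulas: treated = 60/(1 - u); unconfirmed = treated - 60; extra responders = r × unconfirmed; share w = extra/(extra + confirmed responders).

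| u | Treated | Unconfirmed | Extra responders at 15% | w with 24 / 19 confirmed responders |
|---|---|---|---|---|
| 10% | 66.7 | 6.7 | 1.0 | 4.0% / 5.0% |
| 20% | 75 | 15 | 2.25 | 8.6% / 10.6% |
| 30% | 85.7 | 25.7 | 3.86 | 13.8% / 16.9% |

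Two alternatives bracket this:
- At the 0/30 seen in other lymphomas in the earlier trial, w = 0.
- If unconfirmed patients respond as often as confirmed ones (31.7%), rounding up to whole patients gives 7 of 67 and 26 of 86 unconfirmed. That is 2.2 and 8.2 extra responders beside 19, so w is about 10% and 30%.

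**Effect on the median**

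Assume exponential durations, a confirmed median of 1, and a median of h in the added responders. The pooled median t solves

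(1 - w)·2^(-t) + w·2^(-t/h) = 0.5.

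| w | h = 0.5 | h = 2 |
|---|---|---|
| 4% | 0.971 (-3%) | 1.024 (+2%) |
| 17% | 0.883 (-12%) | 1.111 (+11%) |
| 30% | 0.80 (-20%) | 1.21 (+21%) |

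The 30% row pairs with the equal-response case. If those patients do have AITL, h may be near 1 and the shift near zero. The values of h are illustrations; nothing in the documents indicates a direction.

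**The case against.** The strongest case against is that nothing turns on this. Both documents treat time-to-event endpoints as exploratory, and DoR has no test, threshold or power claim. The possible shift is small beside sampling error: with exponential durations and all responders having events, an approximate 95% interval for the median is the estimate times exp(±1.96/√events). That is 0.64 to 1.57 at 19 events and 0.67 to 1.49 at 24, and censoring widens it. A confirmed-only DoR could also be rebuilt by hand from Listings 10.1.2, 10.2.7 and 11.3.6.1.

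All of that is true, and it limits the severity. It does not remove the conflict. PFS and OS have the same exploratory status and follow the protocol's population rule. The shift comes from who is included, so the sampling interval does not account for it. Rebuilding the main DoR population from listings after open-label results are known is a choice the SAP should already have settled.

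It can also be said that 15% is too low for patients who merely lack a specimen. That is fair: an equal response rate raises the share to about 10-30%, though for true AITL patients a larger share need not mean more distortion.

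Finally, the responder set might have been meant as Per Protocol responders. Nothing in the SAP says so, and 4.1 states confirmation where it applies.

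**Conclusion.** The concern holds. Followed as written, the SAP produces its only DoR estimate in a population that Protocol 5.3 and 8.1 do not allow for the main analysis of a secondary endpoint. This is certain from the text.

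The numerical effect is not known. Under the 15% response assumption it is 1 to 4 extra responders, 4-17% of the set, with a median shift between -12% and +11% if their durations are halved or doubled. It is zero if no unconfirmed patient responds, and the share is larger if they respond as often as confirmed patients. The primary ORR, the 19-of-60 criterion, the futility looks and the sample size are unaffected. The change should be made, but the trial's conclusion on its primary endpoint does not depend on it.

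**What to change.** In SAP 4.1, define the main responder set as Per Protocol patients with CR or PR as best response, by independent review for Tables 11.3.2.18 and 11.3.2.20 and by investigator for Tables 11.3.2.19 and 11.3.2.21. This brings in both the eligibility and the confirmation conditions and names the assessor. Carry the change through SAP 4.2, 6.1.2 and 6.2.2. Keep DoR and time to response in all treated responders as a supportive analysis, labelled as such.

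The cost is one changed definition and a filter in four tables, plus supportive versions of those tables. A few responders may leave the main DoR estimate, so its interval would widen slightly; they remain in the supportive analysis. No sample size or power figure changes.
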